
[figure not shown]

Figure 2: Research protocol timeline. Three additional followup phone-calls to assess fatigue will be performed 1, 2, and 4 weeks post the participants' last tDCS treatment.

full list of questionnaires and clinical measures is presented in Table 1. *The primary outcome for this study is trait fatigue measured by the FSS.*

Study Design and a-tDCS Treatment

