This pilot proposal is a randomized longitudinal single-blind sham-controlled intervention. Individuals with PSF will be randomly assigned to the sham or a-tDCS treatment group. Before and after five consecutive days of a-tDCS applied bilaterally over the left and right lower extremity motor cortex, PSF and nervous system and peripheral inflammation will be measured, similar to De Doncker et al. (2021). The tDCS treatment will consist of twenty minutes of 4 mA a-tDCS delivered via two carbon rubber electrodes placed inside sponge pads (1x1 tDCS, Soterix, USA). The current will be ramped up 4 mA over 30 seconds. Each electrode has a surface area of 70 cm², resulting in a current density of 0.06 mA/cm² and a charge density of 1.1 C/cm², which are within current safety guidelines (Bikson et al. 2016). The anode electrode will be centered on the interhemispheric fissure and the central sulcus. This area was chosen due to its previous use in fatigue studies using neuromodulation (multiple sclerosis, Ferrucci et al. 2014; fibromyalgia, Altas et al. 2019; Stroke, De Doncker et al. 2021). The motor cortex is being used more often in neuromodulation studies due to its structural and functional connectivity to cortical and subcortical networks/nodes, e.g. basal ganglia, cingulate cortex. The cathodal electrode will be placed on the nonparetic shoulder. Modeling of cephalic and extracephalic tDCS montages indicates that extracephalic placement of the cathode leads to deeper current flow in the somatosensory cortex (Noetscher et al. 2014). The sham tDCS procedure will be performed in the same manner as active a-tDCS, however, the current will be ramped up and down over 30 seconds (Fridricksson et al. 2018). Figure 2 displays the protocol timeline. Days 2-6 will be consecutive, no more than 36 hours will be allowed between treatment visits. If more than 36 hours elapses the participant will be withdrawn from the study. The measurement of state fatigue, via f-VAS, will be performed before and after each tDCS treatment visit. Follow-up assessments of state and trait fatigue will be performed via phone at one (Follow-up 1), two (Follow-up 2), and four weeks post-treatment (Follow-up 3). The primary study outcome will be the comparison of the FSS scores obtain at baseline (Visit 1) and one week post-tDCS (Follow-up 1).

Neuroimaging

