1. Men and Women, any race or ethnicity, ages 35-80 years
2. 6+ months post-stroke
3. Average Fatigue Severity Score (FSS) ≥ 4 (indicates clinically significant fatigue)
4. Self-reports persistent fatigue for at least the past 6 months
5. Able to walk 10m unassisted

Exclusion Criteria:

1. Absolute contraindications to MRI, TMS, tDCS
2. Inability to follow 3-step instructions
3. Multiple strokes on opposite hemispheres
4. Diagnosis of comorbid neurological conditions (e.g. multiple sclerosis, Parkinson's disease, and dementia)
5. Severe hypertension (resting SBP > 200 mmHg or DBP > 120)
6. Cerebellar or brainstem strokes
7. Hospital Anxiety and Depression Scale (HADS) score > 7 , depression or anxiety
8. Pregnancy

Study Procedures, Materials, and Potential Risks

Source of Materials

Data will be in the form of structured interviews, self-reported rating scales and questionnaires, surface electromyography recorded transcranial magnetic (TMS) evoked potentials, and MRIs. No identifiable information is expected to be collected outside of the consent process. Once consented individuals will be assigned a non-identifiable research ID number that will be used to mark/track collected data.

Research Procedures and Potential Risks

Although unlikely, it is possible that some participants may experience distress when asked questions pertaining to their feelings of fatigue, depression, anxiety, or pain. Some participants may also experience

distress during MRI sessions or TMS assessments. However, previous and ongoing research by our research group indicates that these risks are minimal.

Specific risks, which are all low/minimal, associated with the research procedures are as follows:

tDCS: Commonly reported side effects are as follows: local skin irritation with light itching/tingling/ burning, mild headache, or nausea. There have also been rare cases of mild burns at the procedure site.

TMS: There is a very low risk of a seizure after TMS. The risk of seizure induction by this protocol has been thoroughly assessed and the TMS parameters have been chosen to be well within published safety guidelines for the conduct of TMS studies in human subjects.

Blood Draw / Venipuncture: Risks associated with blood draws include momentary discomfort and/or bruising. Infection, excess bleeding, clotting, or fainting is possible, although unlikely.

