The intervention being studied is a five-session anodal transcranial direct current stimulation (tDCS) intervention delivered over five consecutive days. Measures of post-stroke fatigue and inflammation (central inflammation measured by magnetic resonance spectroscopy and peripheral markers measured via blood analysis) will be made before and after the intervention.

Trial Management. The study will be primarily managed from the Functional Neurostimulation Laboratory ([name], PI) within the Division of Physical Therapy within the College of Health Professions at the Medical University of South Carolina. The target population is adults more than six months post-stroke with clinically present fatigue (average Fatigue Severity Scale > 4).

Data Management and Analysis

The primary outcome of the study is the change in post-stroke fatigue severity (fatigue severity scale (FSS), pre- and post-intervention) and markers of central (measured using magnetic resonance spectroscopy (MRS)) and peripheral (measured via blood analysis) inflammatory markers. Analyses will be guided by the specific hypotheses of the study. Post-hoc exploratory analyses will be conducted with two-tailed tests and more conservative statistical procedures which guard against Type I error (e.g., Tukey tests). All primary hypotheses will be tested at level of significance $\alpha=0.05$. We will also estimate the effect sizes of interest and provide 95% confidence intervals for them.

Quality Assurance

Data quality will be monitored by random inspection of the completed forms by research staff/PI.

Regulatory Issues. All unexpected Adverse Events (AEs) will be reported to the MUSC IRB within 10 working days. Serious AEs (SAEs) will be reported within 24-business hours. Follow-up of all unexpected and serious AEs will also be reported to the IRB. All AEs will be reviewed weekly by the PI and yearly by the IRB. Any significant actions taken by the local IRB and protocol changes will be relayed to NIH. AEs and SAEs occurring during the course of the trial will be collected, documented, and reported in accordance with IRB requirements.

Definition of AE and SAE

Adverse events are defined as any untoward medical occurrence that may present itself during treatment or administration of an intervention, and which may or may not have a causal relationship with the treatment.

Serious adverse events are defined as any medical occurrence that:

- Results in death,
- Is life-threatening,

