If complete information is not available when the initial 24-hour SAE report is disseminated, follow-up information will be gathered to enable a complete assessment and outcome of the event. This information may include hospital discharge records, autopsy reports, clinic records, etc. The research staff will attach copies of source documents to the SAE report for review by the PIs and for forwarding to the NIH program officer as appropriate within 2 weeks of the initial SAE report. In addition, the PIs will provide a signed, dated SAE summary report, which will be sent to the NIH Medical Safety Officer within two weeks of the initial SAE report.

We will report adverse events to the MUSC IRB online as soon as possible, but no later than 10 working days after the investigators first learns of the event. The MUSC IRB AE reporting requirements are as follows: All deaths that occur during the study or 30 days post termination from the study are required to be reported as adverse events even if they are expected or unrelated. Other adverse events are reportable to the MUSC IRB if the AE is unexpected AND related or possibly related AND serious or more prevalent than expected. All three criteria must be met for an AE to be reported to the MUSC IRB. The IRB definition of unexpected is that the AE is not identified in nature, severity or frequency in the current protocol, informed consent, investigator brochure or with other current risk information. The definition of related is that there is a reasonable possibility that the adverse event may have been caused by the device or intervention. Reportable AEs are reviewed by the IRB Chair and reported to the IRB Board at the next meeting.

Trial Safety

The potential risks and benefits and methods to minimize these risks are outlined in Section 3.1, Protection of Human Subjects Section. Protocols for reported AEs and SAEs are outlined above. All unexpected AE and SAEs will be monitored until resolved. A detailed summary of all AEs will be prepared weekly by the research staff and relayed to the PI. Study procedures will follow as much as possible the FDA's Good Clinical Practice Guidelines (www.fda.gov/oc/gcp). All requests by subject's physicians and other medical providers will be referred directly to PI.

DSMP Administration

The PI will be responsible for ensuring participants' safety on a daily basis.

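### The adverse event definition is narrower than the plan's own collection commitment, leaves study procedures unnamed, and comes with no stated way of asking about events after treatment.

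*Combined protocol and SAP*

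**What the plan says.** Safety collection is set out in the Data Safety and Monitoring Plan.

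- **Collection.** Regulatory Issues states that "AEs and SAEs occurring during the course of the trial will be collected, documented, and reported in accordance with IRB requirements".
- **AE definition.** The next heading, Definition of AE and SAE, limits an AE to "any untoward medical occurrence that may present itself during treatment or administration of an intervention". Summary of the Protocol, in the same plan, identifies the intervention as five sessions of anodal tDCS.
- **SAE definition.** It opens "Serious adverse events are defined as any medical occurrence that" and lists seriousness criteria, with no time limit.
- **Ascertainment.** Documentation and Reporting makes research staff responsible for identifying AEs and for the logs and case report forms. It gives no question, visit or schedule for doing so.
- **Relatedness.** The same section calls an event related if the device or intervention may reasonably have caused it. Apart from deaths, the stated IRB reporting criteria require relatedness.
- **Deaths.** "All deaths that occur during the study or 30 days post termination from the study are required to be reported as adverse events", whether or not they are expected or related.
- **Procedure risks.** Research Procedures and Potential Risks covers TMS ("There is a very low risk of a seizure after TMS"), venipuncture (including fainting), MRI and walking tests.
- **Contact after treatment.** The Figure 2 legend says "Three additional followup phone-calls to assess fatigue will be performed 1, 2, and 4 weeks post" the last treatment. Study Design and a-tDCS Treatment says "Follow-up assessments of state and trait fatigue will be performed via phone" at those times.

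**The concern.** The definition decides what is logged as an AE, so a commitment to collect AEs throughout the trial reaches no further than the definition allows. If staff apply the wording as written, a faint at the baseline blood draw or a persistent headache first reported in the second follow-up week need not be recorded. If they apply the collection sentence, both are recorded. The AE count would then depend on who reads which sentence, and on what participants volunteer.

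This matters because the trial is a pilot meant to inform later tDCS studies in post-stroke fatigue, and tolerability is part of what such studies need. There is no independent monitoring board, so safety review rests on what staff log. The death rule raises a related question: reporting starts when the investigators learn of an event, and the plan describes no contact late enough to learn of a death near the end of the reporting window.

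**Working it through.** The plan states no figure to reproduce. The check compares texts and does day arithmetic on the contact schedule.

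**1. Windows side by side**

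| Item | Window stated | Where |
|---|---|---|
| AE collection | Whole trial | Regulatory Issues |
| AE definition | During treatment or delivery of the intervention | Definition of AE and SAE |
| SAE definition | No limit | Definition of AE and SAE |
| Death reporting | Study plus 30 days after termination | Documentation and Reporting |
| Last planned contact | 4 weeks after last tDCS | Figure 2 legend; Study Design |

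The first two rows conflict. The third shows that serious events escape the conflict, so the gap concerns non-serious events.

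**2. Procedures against the definition.** Blood is taken before and after the five treatment days (Blood collection and analysis). Spectroscopy is compared before and after the intervention (Neuroimaging). TMS is done immediately before and after the intervention (Corticomotor Response). Clinical measures, which include the 10 m walk, are assessed before and after the course. None of these is the tDCS intervention. If treatment is read loosely as the treatment week, some post-course procedures may fall inside it. The timeline figure is not available to settle this, but the baseline visit stays outside on either reading. The related test repeats the omission: an unexpected event caused by TMS, MRI or venipuncture could fail it as worded.

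**3. Follow-up weeks against the definition.** Follow-up 3 is at 4 × 7 = day 28 after the last session. From the first session, the treatment course and follow-up span 5 + 28 = 33 days, of which 28 (28/33 = 85%) lie after treatment. This is a share of calendar time, not of expected harm.

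**4. Contact against the death window.** Let T be the day of termination, counted from the last tDCS. The window ends on day T + 30 and the last contact is on day 28, so the shortfall is (T + 30) − 28 = T + 2 days. The plan does not define termination, so a range applies:

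- Termination at the last tDCS (T = 0): window ends on day 30, shortfall 2 days.
- Termination at Follow-up 3 (T = 28): window ends on day 58, shortfall 30 days.
- Withdrawal under the 36-hour rule: the window runs 30 days from withdrawal, and the plan does not say whether the calls still take place. Coverage is not stated.

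**The case against.** The strongest reply is that one phrase is being read literally against its neighbours. The collection sentence comes directly before the definition and covers the whole trial. The SAE definition is open-ended. Staff are told to assess study relatedness, which is wider than relatedness to stimulation. Procedures take place with staff present: nurses draw the blood and a harness is worn for walking tests. AEs are summarised weekly. The death rule is a reporting duty that starts on learning of the event; it does not promise active surveillance. Safety is not part of Aim 1, Aim 2 or the additional analyses, and the intervention is described as minimal risk.

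Much of this stands. A reader might infer that procedure harms, delayed events and post-termination deaths are all beyond what the trial can capture. The documents do not support that: serious events are unrestricted in time, deaths are reportable whatever the AE definition says, and acute procedure events can be seen and logged. A reader might also infer that the calls exclude safety questions. The text says what the calls assess, but does not say that they assess nothing else.

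What does not fall away is the conflict between definition and collection, the related test that omits procedures, and the absence of any stated AE question. Staff presence does not help in the weeks when contact is by telephone.

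**Conclusion.** The point holds as an internal inconsistency combined with no stated active ascertainment. Read literally, non-serious procedure events outside treatment and non-serious events in the 28 days after the last session are not AEs. The last planned contact is 2 to 30 days short of the end of the death-reporting window, and contact after withdrawal is not described.

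Two stronger conclusions are tempting. One is a fixed 30-day gap; that follows only if termination means Follow-up 3. The other is that harms will be undercounted in both arms; the documents give no figure from which to estimate an undercount, and its size would depend on how staff apply the wording.

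The conclusion assumes that intervention means the five tDCS sessions, as the plan's own summary says, and that the timeline figure and case report forms, which are not available, contain no AE query. The primary Fatigue Severity Scale analysis is unaffected. The change is worth making because it improves safety data at very little cost.

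**What to change.** Reconcile the sections in one amendment:

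1. Define an AE as any unfavourable medical event from consent to Follow-up 3, whether or not it is related to stimulation or to a study procedure.
2. Extend the related test to study procedures, naming TMS, venipuncture, MRI and walking tests.
3. Add one open AE question to each of the three scheduled calls.
4. Define termination for the death-reporting rule, and say whether withdrawn participants still receive the calls.

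The same amendment could align the two end-points for following an event: Documentation and Reporting allows follow-up to stop at stabilisation or on leaving, whereas Trial Safety says unexpected and serious events are monitored until resolved.

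The cost is the amendment itself, about one minute per call (24 participants × 3 calls = 72 calls, so about 72 minutes in all), and more minor unrelated events to log. A separate vital-status check for all 24 participants at the end of the 30-day window would close the remaining gap, but it is optional; the documents do not require it.
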